Serum sample for Immunogenicity			X pre-dose								X ¹⁶	X ¹⁶
PGx sample			X pre-dose ¹⁷									
Tumor markers ¹⁸			X							Every 8 weeks		
Disease assessment ¹⁹		X ³								Every 8 weeks	X ²¹	

1. The Follow-up visit should be approximately 28 days after the last dose of study treatment.
2. The Post-study visit should be at least 45 days or 5 half-lives (whichever is longer) after the last dose of study treatment.

3. Within 14 days prior to first dose except for pregnancy test (7 days) and Disease Assessment within 28 days prior to the first dose.
4. Separate pre-screening consent required for fresh biopsy and fresh biopsy is only collected at pre-screening if archived tissue is not available.
5. Fresh pre- and on-treatment tumor biopsy is optional, but strongly encouraged for dose escalation cohorts; if adequate fresh biopsy tumor tissue is acquired during pre-screening, then this does not need to be repeated during the screening period. Archival tumor tissue is not acceptable to serve as pre-treatment tumor tissue.
6. Tumor biopsy is optional on Day 15 for dose escalation cohort subjects and required for the PK/PD cohorts. Biopsy must be collected prior to study treatment administration on Day 15 dose (pre-dose).
7. Collected at progression. Tumor biopsy is optional and only collected for subjects with disease progression on study treatment. The tumor specimen may be collected at any time after study treatment discontinuation, but must occur prior to start of any subsequent anticancer therapy.
8. Perform only in women of child-bearing potential. Serum pregnancy test should be conducted at the Screening, Follow-up, and Post-study visits. Urine pregnancy test should be conducted pre-dose on Day 29 and every 4 weeks from Day 29 in the continuation phase of the study.
9. If the screening visit was completed within 72 hours of the first dose, this assessment does not need to be repeated on Day 1.
10. Collect at pre-dose and at 1, 2, 4, and 6 hours after the start of the first infusion.
11. ECHO is preferred; however, if echocardiography is not available, or if reliable echocardiographic analysis of LVEF is unable to be obtained due to technical factors, a MUGA scan may be performed. Regardless, the method used at Baseline should be used for the remaining assessments in the study. Assessments should be performed more frequently than every 8 weeks if clinically indicated.

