7. Collected at progression. Tumor biopsy is optional and only collected from subjects with disease progression on study treatment. The tumor specimen may be collected at any time after study treatment discontinuation, but must occur prior to start of any subsequent anticancer therapy.
8. Perform only in women of childbearing potential. Serum pregnancy test should be conducted at the Screening, Follow-up, and Post-study visits. Urine pregnancy test should be conducted pre-dose on Day 29 and every 4 weeks from Day 29 in the continuation phase of the study.
9. If the screening visit was completed within 72 hours of the first dose, this assessment does not need to be repeated on Day 1.
10. Collect at pre-dose and at 1, 2, 4, and 6 hours after the start of infusion. For subjects on a weekly dosing schedule, vital signs should be conducted weekly at each dosing visit in clinic.
11. ECHO is preferred; however, if echocardiography is not available, or if reliable echocardiographic analysis of LVEF is unable to be obtained due to technical factors, a MUGA scan may be performed. Regardless, the method used at Baseline should be used for the remaining assessments in the study. Assessments should be performed more frequently than every 8 weeks if clinically indicated.
12. Blood samples for analysis of GSK2849330 concentrations will be collected Day 1: pre-dose and at 1 hour (\pm 15-minute window), 6 hours (\pm 1-hr window) and 24 hours (\pm 8-hour window) after the end of infusion. Pre-dose samples will also be collected on Day 4 (\pm 1-day window), Day 8 (\pm 1-day window) and weekly through Day 57 with additional 1-hour post-dose samples collected on Days 29 and 57. Pre-dose samples will also be collected on Day 71, Day 85 and every 12 weeks thereafter.
13. To be conducted in male subjects only.
14. Whole blood for soluble markers from plasma, serum, and/or cellular markers. Blood samples will be collected on Day 1: pre-dose and at 1 hour (\pm 15-minute window), 6 hour (\pm 1-hour window), and 24 hour (Day 2 [\pm 8-hour window]) after the end of infusion. If a subject's duration of infusion is 3 hours or longer the 6 hour time point is optional. A pre-dose blood sample should be collected on Day 8, Day 15 and Day 29 for all cohorts. An additional sample will be collected at progression.

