GSK2849330 IV infusion ¹⁵			X	X ²²	X	X ²²	X	Everyweek ^{15,22}		
AE assessment			Continuous							
Serum sample for Immunogenicity			X pre-dose						X ¹⁶	X ¹⁶
PGx sample			X pre-dose ¹⁷							
Tumor markers ¹⁸			X					Every 8 weeks		
Disease assessment ¹⁹		X ³						Every 8 weeks	X ²¹	

1. The Follow-up visit should be approximately 28 days after the last dose of study treatment.
2. The Post-study visit should be at least 45 days or 5 half-lives (whichever is longer) after the last dose of study treatment.
3. Within 14 days prior to first dose except for pregnancy test (7 days) and Disease Assessment within 28 days prior to the first dose.
4. Separate pre-screening consent required for fresh biopsy and fresh biopsy is only collected at pre-screening if archived tissue is not available.
5. Fresh pre- and on-treatment tumor biopsy is required; if adequate fresh biopsy tumor tissue is acquired during pre-screening, then this does not need to be repeated during the screening period. Archival tumor tissue is not acceptable to serve as pre-treatment tumor tissue.
6. Tumor biopsy is required on Day 15. Biopsy must be collected prior to study treatment administration on Day 15 dose (pre-dose).
7. Collected at progression. Tumor biopsy is optional and only collected from subjects with disease progression on study treatment. The tumor specimen may be collected at any time after study treatment discontinuation, but must occur prior to start of any subsequent anticancer therapy.

8. Perform only in women of child-bearing potential. Serum pregnancy test should be conducted at the Screening, Follow-up, and Post-study visits. Urine pregnancy test should be conducted pre-dose on Day 29 and every 4 weeks from Day 29 in the continuation phase of the study.
9. If the screening visit was completed within 72 hours of the first dose, this assessment does not need to be repeated on Day 1.
10. For vitals: collect at pre-dose and at 1, 2, 4, and 6 hours after the start of the first infusion. For ECG: collect at pre-dose and 2 hours after the start of the first infusion
11. ECHO is preferred; however, if echocardiography is not available, or if reliable echocardiographic analysis of LVEF is unable to be obtained due to technical factors, a MUGA scan may be performed. Regardless, the method used at Baseline should be used for the remaining assessments in the study. Assessments should be performed more frequently than every 8 weeks if clinically indicated.

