13.7.2. Safety Analyses

The All Treated Population will be used for the analysis of safety data. All serially collected safety endpoints (e.g., laboratory tests, vital signs, ECGs) will be summarized according to the scheduled, nominal visit at which they were collected and across all on-treatment time points using a "worst-case" analysis.

DLTs will be listed for each subject and summarized according to GSK IDSL standards. All other relevant safety data will be listed and summarized according to the GSK IDSL standards as well. Complete details of the safety analyses will be provided in the RAP.

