# 7.1. Data Display Treatment and Other Subgroup Descriptors

Treatment groups with the same dose and the same administration frequency will be combined in final analyses as displayed in the table below. All data will be summarized or listed by the treatment group except PK concentration data, which will be listed by part and dose cohort.

Treatment	Treatment Description	Treatment Label / Column Header
Code		
1	Part 1 DE Cohort: 1.4 mg/kg weekly	Part 1 Cohort: 1.4 mg/kg weekly
2	Part 1 DE Cohort: 3 mg/kg every 2 weeks	Part 1 Cohort: 3 mg/kg every 2 weeks
3	Part 1 DE & PK/PD Cohort: 10 mg/kg every 2 weeks	Part 1 Cohort: 10 mg/kg every 2 weeks
4	Part 1 DE & PK/PD Cohort: 30 mg/kg every 2 weeks	Part 1 Cohort: 30 mg/kg every 2 weeks
5	Part 1 DE & PK/PD Cohort: 30 mg/kg weekly	Part 1 Cohort: 30 mg/kg weekly
6	Part 1 PK/PD Cohort: 3 mg/kg weekly	Part 1 Cohort: 3 mg/kg weekly
7	Part 2 Expansion Cohort: 30 mg/kg	Part 2 Cohort: 30 mg/kg

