#### ECG

As per the protocol, all ECGs will be single assessments unless clinically significant abnormality is observed, in which case repeat ECG twice more, for a total of 3 ECGs within approximately 5-15 minutes. Manual calculation for all 3 ECGs should be done using Fridericia's formula (QTcF=QT/RR1/3) in view of the complex relationship between QT and RR.

Any clinical decisions should be based on the average of all three ECGs.

The following parameters will be derived if applicable, where they are derived to the same number of decimal places as the raw data.

Variable	Description	Algorithm
RR	R RR interval	
 
If QTcB is machine read and QTcF is not provided, then: RR = [(QT/QTcB)^(2)]*1000
 
If QTcF is machine read and QTcB is not provided, then: RR = [(QT/QTcF)^(3)]*1000
 
If ECGs are manually read, the RR value preceding the measured QT
 

		interval should be a collected value Do Not Derive.
QTcB	QTc interval, using Bazett's correction	
 
If not provided in dataset, derive:
 
QTcB = QT / ((RR/1000)^1/2), where RR is in msec
 

QTcF	QTc interval, using Fredericia's correction	
 
If not provided in dataset, derive:
 
QTcF = QT / ((RR/1000)^1/3), where RR is in msec
 

A summary of the number and percentage of subjects who had normal and abnormal (clinically significant and not clinically significant) ECG findings will be displayed by part, dose group, and scheduled visits as well as for the worst case post-baseline. See Section 9.4.2 for details.

In addition, ECG interval values will be also be summarized.

Listings of abnormal ECG findings and a listing of ECG values will be provided.

A figure plotting the baseline QTc and the worst-case post-baseline values will be produced. The figure will have reference lines at 450 and 500 msec for both the ordinate and the abscissa axes. There will be diagonal reference lines at equality (i.e. a 45 degree line), at equality plus 30 msec, and at equality plus 60 msec.

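### Worst-case QTcF and ECG displays set Part 1 (four post-dose Day 1 ECGs) beside Part 2 (one) with no restriction to common times, which tilts the worst case toward Part 2 by an unknown amount

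*Protocol*

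**What the plan says.** Change in ECG is part of the primary endpoint in both parts (Protocol 2.1 and 2.2). The Day 1 ECG schedule differs between them.

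- **Part 1** (Protocol 7.1, footnote 10 of Tables 7, 8, 9 and 11): "Collect at pre-dose and at 1, 2, 4, and 6 hours after the start of the first infusion". Table 10, for the weekly PK/PD cohorts, has "Collect at pre-dose and at 1, 2, 4, and 6 hours after the start of infusion". The footnote is attached to both the vital-signs row and the ECG row.
- **Part 2** (Table 12, footnote 10) keeps the four times for vital signs, but: "For ECG: collect at pre-dose and 2 hours after the start of the first infusion".

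After Day 1, Tables 7 to 10 and Table 12 have the same ECG visits: Day 15, Day 29, every 4 weeks, and Follow-up. The every-3-week schedule (Table 11) differs, but no treatment group in SAP 7.1 uses it.

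On analysis, Protocol 13.7.2 says that serial safety data "will be summarized according to the scheduled, nominal visit at which they were collected and across all on-treatment time points", the latter as a worst-case analysis. SAP 7.1 says "All data will be summarized or listed by the treatment group except PK concentration data", and its list of column headers puts "Part 2 Cohort: 30 mg/kg" after six Part 1 cohorts, two of which also receive 30 mg/kg. The ECG part of SAP 12.8 says "ECG findings will be displayed by part, dose group, and scheduled visits as well as for the worst case post-baseline". SAP 19.1.3 lists the worst-case QTcF tables (11.34, 11.35), the ECG findings table (11.38) and the figure of baseline against worst post-baseline QTcF (11.2), all on the All Treated population. SAP 9.2.8 lets unscheduled readings into worst-case sections. Neither document restricts the worst case to times that both parts share, or notes that the schedules differ.

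**The concern.** A worst case is a maximum over whatever was collected. Adding reading times can raise a maximum but never lower it. With the same drug, the same subjects and the same time on treatment, the Part 1 schedule therefore gives a worst case at least as high as the Part 2 schedule, and on average a higher one.

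This touches the main question of Part 2, which is safety in a larger population at the chosen regimen. A reader who sees fewer worst-case QTcF increases in the Part 2 column than in a Part 1 column at the same dose may take that as reassurance, when part of the difference comes from three fewer ECGs on Day 1.

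**Working it through.** The plan states no figure on this point, so there is none to reproduce. The check is a count of ECGs, followed by a calculation under stated assumptions.

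**Step 1: scheduled post-baseline ECGs per subject.** Baseline is the Day 1 pre-dose value (SAP 9.2.6). The count is Day 1 post-dose readings + later visits + Follow-up.

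| Last visit | Later visits, with Follow-up | Part 1 | Part 2 |
|---|---|---|---|
| Day 29 | 15, 29, Follow-up = 3 | 4 + 3 = 7 | 1 + 3 = 4 |
| Day 57 | 15, 29, 57, Follow-up = 4 | 4 + 4 = 8 | 1 + 4 = 5 |
| Day 169 | 15, 29, then 57 to 169 (five visits), Follow-up = 8 | 4 + 8 = 12 | 1 + 8 = 9 |

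The difference is always three readings, so its weight shrinks as treatment goes on.

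**Step 2: size with no drug effect.** The documents give neither the within-subject variability of QTcF nor the correlation of same-day readings, so both are assumptions. Let *s* be the SD of a single reading about the subject's mean (8 to 15 ms). Let *ρ* be the share of that variance common to all Day 1 readings, including the pre-dose baseline (0 or 0.5). Let *m* be the number of Day 1 post-dose readings (4 or 1) and *L* the number of later readings. The threshold is 31 ms, the lower limit of the first increase category in SAP 9.4.2. With independent D ~ N(0, ρs²) and E ~ N(0, (1−ρ)s²):

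P(worst increase ≥ 31) = 1 − mean over D and E of { Φ[(31 + E)/(s√(1−ρ))]^m × Φ[(31 + D + E)/s]^L }

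Results for Day 57 plus Follow-up (L = 4), by numerical integration. The last column is 1 − (Part 2 / Part 1), from unrounded values:

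| s (ms) | ρ | Part 1 | Part 2 | Part 2 lower by (relative) |
|---|---|---|---|---|
| 8 | 0 | 1.96% | 1.33% | 32% |
| 8 | 0.5 | 1.11% | 1.10% | 1% |
| 10 | 0 | 7.7% | 5.5% | 29% |
| 10 | 0.5 | 4.9% | 4.7% | 4% |
| 15 | 0 | 28.9% | 22.5% | 22% |
| 15 | 0.5 | 22.6% | 20.5% | 9% |

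A simulation of 1,000,000 subjects agrees to within rounding. In it the mean worst change was lower in Part 2 by 1.4 ms (s = 8, ρ = 0.5: 10.7 against 9.3) to 3.9 ms (s = 15, ρ = 0: 21.4 against 17.5). For increases above 60 ms at s = 15 it gave 1.5% against 1.0% (ρ = 0) and 0.85% against 0.84% (ρ = 0.5).

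**Step 3: what this means in subjects.** Protocol Table 3 plans at least 3 dose-escalation subjects and up to 3 PK/PD subjects per Part 1 regimen. With six subjects and s = 10, the expected difference is 6 × (0.077 − 0.055) = 0.13 of a subject at ρ = 0, and 6 × (0.0488 − 0.0471) = 0.01 at ρ = 0.5.

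**The case against.** The case for leaving the plan alone has real substance.

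- *No comparison is planned.* Protocol 13.5.1 and SAP 7 exclude formal comparisons, and by-visit ECG summaries compare like with like at the shared times. Both points stand. They limit the issue to the worst-case rows and Figure 11.2, but they do not make those like-for-like.
- *The effect may be negligible.* Readings a few hours apart on one day are plausibly correlated, and the gap then nearly disappears at the lower SDs. This stands: independence gives the upper end of the range and should not be quoted alone.
- *Other differences matter more.* Time on treatment, unscheduled ECGs and very small Part 1 cohorts all drive worst-case counts. This is true, but they add to the sampling difference and do not remove it.
- *Averaging rules might already deal with it.* SAP 9.2.8 averages repeat readings at the same planned time. The readings at 1, 2, 4 and 6 hours are different planned times, so that rule does not level the schedules.

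Two stronger readings are tempting. A reader might infer that Part 2 *will* show fewer QTc events because of sampling. The documents support only a tendency with all else equal. A reader might also infer that the dropped hours contain the peak, so that Part 2 misses a real effect. Table 5 gives a median tmax of 1 h (range 1 to 6) at 3 and 10 mg/kg. The post-dose PK samples are timed from the end of a 1-hour infusion, so if Table 5 uses those nominal times, the median falls about 2 hours after the start, which is the ECG time that Part 2 keeps. The documents describe no time course for a QTc effect, and Protocol 1.2.3 reports none in the monkey study.

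**Conclusion.** The point holds as a one-directional lack of comparability in the worst-case displays. Part 1 has three more scheduled post-baseline ECGs per subject than Part 2 at any equal time on treatment (7 against 4 at Day 29, 8 against 5 at Day 57, both with Follow-up). The SAP takes the maximum over all of them and shows both parts together without a caveat.

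The size cannot be settled from the documents. With no drug effect and an SD of 8 to 15 ms, the chance of a worst-case increase of at least 31 ms by Day 57 plus Follow-up is about 1% to 32% lower in relative terms in Part 2, and the mean worst change is about 1.4 to 3.9 ms lower. The low end assumes that half the variance is shared within Day 1, and the high end assumes independent readings. For increases above 60 ms the absolute difference is at most about half a percentage point under these assumptions.

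This is a cheap improvement to a primary-endpoint safety display, not a flaw that invalidates it. It does not show that Part 2's ECG monitoring is inadequate.

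**What to change.** In the ECG part of SAP 12.8, and in Tables 11.34, 11.35, 11.38 and Figure 11.2:

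1. Derive any worst case shown across parts only from the scheduled times that both parts have: Day 1 at 2 hours, Day 15, Day 29, every 4 weeks, and Follow-up. For a subject whose last visit is Day 57, this gives 5 scheduled ECGs in either part.
2. Keep the all-time-point worst case, including the other Day 1 hours and unscheduled ECGs, within each part separately. Show the number of ECGs per subject with it, and add a footnote that it is not comparable across parts because the Day 1 schedules differ.
3. State that the common-time row should be read with exposure. ECGs every 4 weeks accumulate with time on treatment, and the restriction does not equalise that.

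The cost is SAP wording and one extra row or table per display. The cross-part row uses fewer Part 1 readings, but the within-part display keeps them all. No ECG is added or dropped, and the protocol schedule does not change.

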7.2. Demographic/Medical History and Baseline Assessments

Demographic data will include gender, age, race, height, and weight. Medical, surgical, and treatment history including date [month (if available) and year] of first diagnosis, best response to prior systemic therapy, histology, molecular characteristics and current sites of disease will be taken as part of the medical history and disease status. Details concerning concomitant medication will be recorded starting from screening through the follow-up visit. At a minimum, the drug name, route of administration, dose and frequency of dosing, along with start and stop dates/times should be recorded.

7.2.1. Critical Baseline Assessments

Cardiovascular medical history/risk factors will be assessed at baseline.

7.3. Safety Evaluations

Measurements used to evaluate safety will include physical examinations, vital signs (BP, temperature and pulse rate), 12-lead ECGs, echocardiography, clinical laboratory tests, , and monitoring for AEs. Planned time points for all safety assessments are provided in the Time and Events Tables (Section 7.1).

Additional, unplanned safety assessments may be performed during the course of the study as clinically indicated in the judgment of the investigator. Additional time points for safety tests may also be added during the course of the study based on newly available data to ensure appropriate safety monitoring.

7.3.1. Physical Examinations

A complete physical examination will include assessments of the head, eyes, ears, nose, throat, skin, thyroid, neurological, lungs, cardiovascular, abdomen (liver and spleen), spine and long bones, lymph nodes and extremities. Height (at screening only) and weight will also be measured and recorded.

7.3.2. ECOG Performance Status

The performance status will be assessed using the ECOG scale ([Appendix 3](#)) as specified in the Time and Events Tables (Section 7.1).

7.3.3. Vital Signs

Vital sign measurements will include systolic and diastolic blood pressure (BP), temperature, and pulse rate. Vital signs will be measured more frequently if warranted by clinical condition of the subject. On days where vital signs are measured multiple times, temperature does not need to be repeated unless clinically indicated. Refer to the SPM for details regarding measurement of vital signs.

If a subject develops a fever within the immediate post-infusion period, refer to Section 3.9.1 and Section 3.9.2 for management of infusion reactions and allergic reactions.

7.3.4. Electrocardiogram

Single 12-lead ECGs will be obtained at designated time points during the study using an ECG machine that automatically calculates the HR and measures PR, QRS, QT, and QTc intervals. At each assessment a 12-lead ECG will be performed by qualified personnel at the site after the subject has at least a 5-minute rest and is in a semi-recumbent or supine position.

All ECGs will be single assessments unless clinically significant abnormality is observed, in which case repeat ECG twice more, for a total of 3 ECGs within approximately 5-15 minutes. Manual calculation for all 3 ECGs should be done using Fridericia's formula ($QTcF=QT/(RR)^{1/3}$) in view of the complex relationship between QT and RR. Any clinical decisions should be based on the average of all 3 ECGs.

Refer to Section 3.8.2 for QTc withdrawal criteria.

Refer to the SPM for details regarding ECG procedures.

7.3.5. Echocardiogram and/or Multi-gated Acquisition (MUGA) Scans

ECHO will be performed to assess cardiac ejection fraction as noted in the Time and Events Tables Section 7.1. Should electrocardiography not be available or if echocardiographic analysis of LVEF is unable to be obtained due to technical factors, a MUGA scan may be performed. However, whichever method is used at baseline should be used for the remaining assessments in the study. Additional ECHO assessments may be performed if clinically warranted. The evaluation of the echocardiographer should include an evaluation for LVEF.

Copies of all ECHOs performed on subjects who experience an absolute decrease >15% in LVEF compared to baseline or an absolute decrease >10% in LVEF compared to baseline concurrent with LVEF <50% may be required by GSK for review.

